2.1.3. Study Cohorts / Arms / Groups

Pre/post-intervention design. Participants' tobacco use will be compared at two timepoints: Enrollment, and End of treatment.

2.1.4. Scientific Justification for Study Design

This study is a pilot to test feasibility of the app among patients from the Stanford Cancer Center who smoke cigarettes daily. There will be 20 kits available for testing feasibility. Outcomes will be assessed pre-intervention and post-intervention.

Factors that indicate feasibility will include (i) interest among our patient population in using the app, which will be offered at no cost; (ii) among those patients who are interested, that they are able to onboard and make use of the app; and (iii) patient ratings of recommending the app to others. Feasibility metrics would be at least (i) 20% interested in using the app; (ii) 75% of interested patients onboarded and using the app; and (iii) 70% recommending the app to others. Efficacy goals will be examining tobacco use reduction and quitting with goals of at least (iv) 50% reducing tobacco use and 10% quitting. Not feasible would be indicated by **less than** (i) 20% interested in using the app; (ii) 75% of interested patients onboarded and using the app; and (iii) 70% recommending the app to others.

Given the novelty of the program (virtual reality app) and our older patient population, we are interested in seeing do patients have interest in using the program, are they able to onboard at a distance (from home), do they make use of the app, and would they recommend the app to others. We also will examine whether they reduce or quit their tobacco use. If the metrics above are met, we would consider adding MindCotine to the choices available.

2.1.5. Treatment Assignment

Open-label: No study blinding.

2.1.6. Justification for Dose(s)

N/A.

2.1.7. End of Study Definition

A participant is considered to have completed the study if they have completed their end of treatment assessment after the 6-week intervention.

2.2. Objectives

Learning whether MindCotine is a feasible smoking cessation option among 20 patients from the Stanford Cancer Center who smoke cigarettes daily. Learning whether less tobacco use is associated with utilizing multiple tobacco cessation options.

2.2.1. Primary Objective

Learning whether MindCotine is a feasible smoking cessation option among 20 patients from the Stanford Cancer Center who smoke cigarettes daily.

2.2.2. Secondary Objective(s)

Learning whether less tobacco use is associated with utilizing multiple tobacco cessation options.

2.3. ClinicalTrials.gov Registration, Outcomes, and Results

This study is not an applicable clinical trial (ACT) per FDAAA 2007, does not meet the criteria for mandatory study registration at ClinicalTrials.gov, does not have direct NIH funding, and will not be posted in the Stanford Clinical Trials Directory. Therefore, this study will not be registered at ClinicalTrials.gov.

3. SUBJECT SELECTION

3.1. Eligibility Criteria and Participant Eligibility Checklist

Inclusion and Exclusion Criteria are provided on the Eligibility Checklist which may be extracted from this document for use in screening potential subjects.

The Participant Eligibility Checklist must be completed in its entirety for each subject prior to registration (see Section 3.4 Registration / Enrollment). The completed, signed, and dated checklist is retained in the subject's record. Screening results will be collectively documented on the Study Participant Log (see references in Appendix A).

Participant Eligibility Checklist

I. Protocol Information

Protocol Title:	Stanford Tobacco Treatment Services – Virtual Reality Treatment for Smoking Cessation
Principal Investigator:	[name]

II. Subject Information

Subject name / Unique ID:	/

III. Eligibility Criteria

3.1.1. Inclusion Criteria

1. Daily or some day cigarette smoker (>9 cigarettes/week)			Identified as a cigarette smoker in Epic; Phone s
2. Age 18+			18+ on Epic
5. Available to interact with a smartphone app for 6 weeks			Phone screen
6. Available to complete the EOT assessment at end of 6-weeks			Phone screen
8. Confirm phone, email, address during consent			ICF, Epic

3.1.2. Exclusion Criteria

Prospective Participants Must NOT Meet ANY of These Exclusion Criteria	Yes		Supporting Documentation

* All subject files must include supporting documentation to confirm subject eligibility.

V. Statement of Eligibility

By signing this form of this trial I verify that this subject is:

eligible for participation in the study ineligible for participation in the study

Signature:

Signature:

3.1.3. Lifestyle Considerations

- No Restrictions. The participant can access the app at any time of day. Interaction with the app is estimated to take 10 min per day.

3.1.4. Screen Failures

Participants consent to participate in the clinical trial, but who do not meet 1 or more Eligibility Criteria during the screening procedures are considered Screen Failures. Screen Failures will not be considered enrolled subjects, although they **WILL** be tracked on the Screening Log (with reason for ineligibility) and in the OnCore study management system. Individuals who do not meet the criteria for participation in this trial, ie, screen failure, because of **smartphone compatibility** may be rescreened. Potential subjects who are re-screened will be assigned the same sequence number and OnCore subject identifier as for the initial screening. If a screen failure occurs and the person requested their information to not be kept, the decision will be honored but the screen will count towards the number of screen failures of that day.

3.2. Recruitment and Retention Procedures

3.2.1. Recruitment

Potential participants may be identified by the following methods:

- Review of the medical records of new or existing oncology patients for potential subjects who meet eligibility criteria.
 - Patients who use tobacco are identified from Stanford Cancer Clinics, and our Tobacco Treatment Specialist reaches out to them to engage in tobacco cessation. The VR pilot will be brought up as an option (phone script available). If a patient is interested in the VR treatment option, patients will be going through a phone screen (with consent) on whether they would be able to use the VR intervention (e.g. smokes, smartphone compatibility, language fluency), and if eligible and interested, proceeds to the informed consent process. After that, the intervention kit will be mailed to the participant, the participant interacts with the intervention and is followed up with an end-of-treatment survey after the 6-weeks.

3.2.2. Retention Procedures

None. After enrollment, participants will be contacted at the end of the 6-week intervention. Unless the participant reaches out to the team during the intervention period, there is no expected contact with the participant until the end of the 6-week period.

3.3. Informed Consent Process

Study participants will provide written informed consent prior to the conduct of any study-specific procedures in accordance with institutional policies via online. For Spanish speaking patients, the consent form will be translated by Stanford Hospital Translation Services prior to recruitment. The study is completely remote, and the consent form will be provided via online link.

3.4. Registration and Enrollment

3.4.1. Subject Registration Procedures

All subjects who provide informed consent for this study will be registered in the Stanford OnCore Enterprise Research System (“OnCore”) database within 5 days of the date of consent, regardless of the outcome of any eligibility screening.

Subject identification numbers will be sequentially assigned **for the entire study**.

The Stanford study team will review eligibility for each subject, and provide the 3rd signature on the Eligibility Checklist, which confirms and documents eligibility. Once confirmed by Stanford, the subject will be promptly registered in OnCore (within 5 business days) and the subject’s OnCore accrual status will be updated. At this time, the subject can begin study treatment procedures.

_____ | @stanford.edu

[name]
[contact]
[contact]

3.4.2. Subject Enrollment Procedures

For this study, a subject is enrolled on the study when registered per Section 3.4.1; has meet eligibility per the screening procedures; and has been otherwise accepted into the study.

Each week, the Tobacco Treatment Specialist generates an Edge Report that lets them know which patients have been identified as a tobacco user at the Stanford Cancer Center or satellite clinics. Any patients referred to the Tobacco Treatment team by a nurse practitioner or doctor of medicine will be included for outreach as well. Of the patients identified as a tobacco user and seen at the Stanford Cancer Center or satellite clinics, 74% are reached for initial outreach by the TTS. Of those reached, 34% engage in treatment. The study will be offered to all the patients reached at this initial outreach. The initial outreach involves contacting the patients with up to two phone calls. We do not know if these patients are interested in the app; Interest in the app will be considered for feasibility. We expect the study to be brought up as an option, along with the other tobacco treatment offerings (i.e. behavioral counseling, cessation medication), during a phone call with each patient up till enrollment stops.

If a patient expresses interest in the study, they will be directed to the phone screen conducted by the TTS. To enroll in the study, patients must pass the phone screen, and if eligible, sign the informed consent form on via Adobe Sign. Enrollment will stop after 20 informed consent forms have been signed. Enrollment will not focus on certain tumor types.

Should any interest in the study come up after we’ve finished enrollment, we’ll note it but also inform the patient that we have filled enrollment for the study. This may happen if a patient who has screened, but has not signed the informed consent form, asks for some time to think about participating in the study. Patients who ask for some time to consider participation will be told only 20 spots are available and may fill; No spots will be held to wait on a response.

4. STUDY INTERVENTION

4.1. Investigational Drug / Device / Procedure: *MindCotine*

4.1.1. Name

MindCotine

4.1.2. Dose and Administration

Mobile app program. Can be used at any time. Duration intervention is estimated up to 10min a day for 6 weeks.

4.1.3. Regulatory Status of MindCotine

MindCotine is approved for marketing in the United States, for the indication(s) of tobacco cessation. This indication includes is for the use described in this study. Regulatory authorization to conduct this study is pursuant the definition of an IND-Exempt study.

4.1.4. MindCotine Preparation, Handling, Storage, and Accountability .

4.1.4.1. Acquisition and Accountability

MindCotine will send 20 VR kits to the Stanford team. These kits will include the MindCotine brochure (details what to expect with the VR smoking cessation program), cardboard headset, wristbands, stickers, and an activation code for accessing the full program. The program is an app is downloadable from the app store. These kits will be mailed out by the Stanford team to the 20 participants. Once the kit reaches the participant, that kit belongs to the participant; Nothing needs to be returned.

4.1.4.2. Formulation, Appearance, Packaging, and Labeling

MindCotine is packaged as a mobile app program. The app is downloadable from the app store. The VR kit MindCotine has for their users primarily is for providing a cardboard headset so an immersive VR environment can be achieved, and the activation code provides full access to the program.

4.1.4.3. Storage and Stability

The MindCotine app is available on mobile. No particular storage requirements aside from space for the app on the phone. The cardboard headset should be durable in most environments. Neither the phone nor cardboard headset should get wet.

4.1.4.4. Preparation

Preparations include downloading the app and utilizing the activation code; and assembling the cardboard headset from the VR kit. MindCotine is available for support if the participant decides to reach out to them. Participants can always reach out to the study team for questions.

4.1.5. Investigational Agent Supply

MindCotine is supplying the VR kits. The Stanford team will be handling the shipping to participants.

The mailing address and local contact phone number for MindCotine Inc. is:

Name: MindCotine, Inc.

Address: [name]

[contact]

4.1.5.1. Investigational Agent Ordering

MindCotine is supplying the VR kits. The Stanford team will be directly handling the shipping to participants. The Stanford team will coordinate shipping details with MindCotine.

The mailing address and local contact phone number for MindCotine Inc. is:

Name: MindCotine, Inc.

Address: [name]

[contact]

4.2. Comparator / Control Agent:

N/A

5. TREATMENT PLAN

5.1. Treatment Assignment

After the subject is determined to be completely eligible to participate in the study, the OnCore sequence number, a unique subject identifier, will be sequentially assigned. There is no randomization or blinding

5.2. Treatment Dose

N/A. No dosage.

5.3. Treatment Schedule

Comparison is post-treatment to pre-treatment among the participants.

5.4. Treatment Duration

The intervention period is 6-weeks. Estimated participation of 10 min per day interacting with the program.

5.5. Subject Medication Diary

N/A.

5.6. Pre-Treatment Criteria

Participants will undergo a phone screen before eligibility is determined. Participants should be daily cigarette smokers, English or Spanish fluent, have a compatible smartphone, available to complete survey assessments, willing commit to the intervention, and not have a history of epilepsy.

5.7. Dose Modifications and Dose-limiting Toxicities

Adverse event documentation and reporting is described in Section 7.

N/A, not a drug. If VR sickness is experienced during the intervention, the participant can remove themselves from the environment by taking off the headset.

5.8. Concomitant Medications, Procedures, and Supportive Care Guidelines

N/A

5.9. Criteria for Removing Subjects from Study Intervention and/or Study

Subjects are free to withdraw consent and discontinue participation in a study at any time without prejudice to further treatment. The investigator may discontinue a subject from treatment intervention or the entire study for medical or administrative reasons. The following reasons may lead to discontinuation from the study intervention or the entire study.

- Withdrawal of consent
- Study non-compliance
- Investigator discretion

If the subject elects to withdraw consent from further treatment with the study intervention, or is withdrawn by the investigator, it will be confirmed and documented if the subject will consent to continue to be followed per protocol, if applicable. The rationale for the investigator's decision to discontinue treatment will be clearly documented.

5.10. Duration of Follow-Up

After completion of treatment (ie, date of last treatment / intervention *6-weeks post enrollment*) subjects will be followed up soon after with an end of treatment survey after the intervention or removal from study or until death, whichever occurs first. Should the study team learn of any severe adverse events during the intervention period, [name] will be notified and the team will proceed according to her instructions.

5.11. Study Completion or Discontinuation

The study will be complete when the last study data, including all follow-up data, has been collected, and analysis is complete. This is expected to occur within a couple of months after the final study participant has completed their end of treatment assessment, which includes questions on tobacco use, satisfaction with the program, likelihood of recommending the program, and questions on whether VR side effects were experienced.

Subjects will no longer be followed or subject data collected as part of this study once the study is complete per this section.

Conditions may be discovered during the conduct of the study by the investigator, regulatory authorities, or other oversight bodies that indicate that the study should be terminated prematurely. The reasons that may warrant termination include, but are not limited to:

- The study is determined to be non-feasible, including inadequate accrual
- Determination of unexpected, significant, and/or unacceptable risk to participants
- Insufficient compliance to protocol requirements
- Data that are not sufficiently complete and/or evaluable
- Determination of futility
- Business decision by the Principal Investigator, institution, or funding source, etc

Written notification will be provided by the investigator to the IND/IDE sponsor, the funding entity, and regulatory authorities as appropriate, including the IRB of record.

6. STUDY PROCEDURES AND ASSESSMENTS

6.1. Schedule of Events

Schedule of Events

	screening			Wk 3		Wk 5			Wk 8		Wk 10	Wk 11
Phone consent	X											
Smartphone compatibility	X											
TTS cessation services	X											
Notes	Ideally the EOT survey is completed as close as possible to 6-weeks. It's possible the study team will tempt follow up for up to three times after the intervention period.											
Recruitment			X		X			X		X		

6.2. Description of Procedures and Assessments

6.2.1. Efficacy Assessments

1. Patients who use tobacco are identified as part of the Tobacco Treatment Program. The Tobacco Treatment Specialist reaches out to these patients and offers tobacco cessation resources, and the pilot study will be offered as a part of this. Recruitment of 20 participants is estimated to take approximately 3 months.
2. If a patient expresses interest in the pilot study, they will go through a phone screen consent and questionnaire. Inclusion criteria includes daily or some day cigarette smoking, English or Spanish fluency, have compatible smartphone, willing to commit to the intervention and complete the surveys, and no history of epilepsy.

3. Informed Consent: If a patient is eligible for the study, and would like to proceed, they will go through an informed consent process provided via online link. The Tobacco Treatment Specialist will be available to go through the consent form with the patient. If signed, they will be enrolled in the pilot study, and a copy of the signed consent form can be provided via secure email or by mail.
4. Within two business days of the informed consent, a study research team will keep track of signed consents and keep track of participants, including demographics, any tobacco cessation resources the participant also wanted to use, date of screening, when the kit was mailed out, and when end of treatment will be.
5. Within two business days of the informed consent, the study team will mail out a VR kit to the participant. The VR kit should reach the participant in 3-5 business days.
6. Once the VR kit is received, the participant can have full access to the MindCotine app and start the intervention.
7. The participant interacts with the app for 6-weeks.
8. After the 6-week intervention, the study team reaches out to the participant to complete the end of treatment survey. If the team is unsuccessful with reaching the participant after 3 attempts, the participant will be considered “lost to follow up”. The end of treatment assessment will include questions on tobacco use, satisfaction with MindCotine, likelihood of recommending MindCotine to others, and whether VR side effects were experienced.
9. Any adverse effects learned of will be tracked.
10. MindCotine will provide user app data from the 20 participants.
11. The study team will link the app data to the survey data and remove identifiers.
12. [name] will conduct data analysis.
13. The study team will provide a summary of outcomes to MindCotine.
14. The study team will decide on whether to invest in MindCotine as a tobacco treatment option for patients.
15. [name] may disseminate outcomes.

6.2.2. Safety and Other Assessments

During screening, patients who have a history of epilepsy are not eligible for the pilot study. The VR environment may be triggering for these patients.

At end of treatment, VR side effects will be assessed.

We do not anticipate serious adverse events as a result of an app designed for smoking cessation. Should any become known to the team, [name] will be notified within 24 hours upon learning of that information, and the team will proceed according to her directions. All SAEs will be documented. [name] is a licensed clinical psychologist and has led multiple clinical trials.

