1.3. Potential Risks and Benefits

1.3.1. Known Potential Risks of MindCotine

The virtual reality simulation could potentially trigger seizures. Those with a history of epilepsy should not use this treatment option.

There is also the possibility of side effects from the virtual reality simulation. Symptoms may include dizziness, disorientation, nausea, sweating, or headaches.

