7.4.1. Case Report Forms for Adverse Event Reporting

Both SAEs and non-serious adverse events will be described in source documentation and listed on study-specific Case Report Forms (CRFs or eCRFs).

Adverse events will be recorded on a log (see references in Appendix A) providing the unique subject identifier, event preferred term, CTCAE body system, date of occurrence, date of resolution; and type of resolution. All signs, symptoms, significant laboratory findings, AND diagnoses should be recorded, regardless of relationship, except as described in this document. A single “overarching” diagnosis should not be solely entered as the adverse event term in lieu of the full list of observed signs, symptoms, and significant laboratory findings, which may include the diagnostic preferred term.

Types of resolution are:

- “Resolved,” ie, to Grade 0 (or baseline if a pre-existing condition)
- “Continuing” and stable (includes downgrades from a higher grade to a lower grade)
- “Deceased” (due to any cause while on-study)
- Lost-to-follow-up.
- **NOTE:** “Hospitalized” is not an outcome.

Any pre-existing condition that worsens in severity or frequency should be recorded as a new adverse event, except as described in this document.

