4. Are you currently using any quit smoking medications?	
 a. Chantix b. Bupropion c. NRT (patches, gum, lozenges, spray) 	Original

If still smoking –
 
5. During the past 6 weeks, have you stopped smoking cigarettes for one day or longer because you were trying to quit smoking?
	
 a. Yes, stopped smoking cigarettes for one day more in an attempt to quit b. No, did not stop smoking cigarettes for one or more 	ASPiRE (modified)
6. How would you rate the MindCotine program?	
 a) Excellent b) Good c) Fair 	CSQ-8 (adapted)
7. If a friend was in need of quitting smoking, would you recommend MindCotine to them?	
 a) No, definitely not b) No, I don't think so c) Yes, I think so d) Yes, definitely 	CSQ-8 (adapted)
8. Did you experience any of the following when using the MindCotine app?	
 1. Dizziness None Mild Moderate Severe 2. Nausea None Mild Moderate Severe 3. Disorientation None Mild Moderate Severe 4. Sweating None Mild Moderate Severe 5. Headache None Mild Moderate Severe 	Original for assessing side effects of VR

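### The five VR symptoms are rated only at end of treatment, so study-collected ratings cannot reliably separate symptoms already present from new or worsened ones

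*Combined protocol and SAP*

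**What the plan says.** Section 1.3.1 names the expected side effects of the headset sessions: "Symptoms may include dizziness, disorientation, nausea, sweating, or headaches". Item 8 of the end-of-treatment questionnaire in 13.2.1 lists the same five symptoms, each rated from None to Severe, under the question "Did you experience any of the following when using the MindCotine app".

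The timing is a single point. Section 6.2.2 says "At end of treatment, VR side effects will be assessed", and 6.2.1 (item 8) lists among the end-of-treatment topics "likelihood of recommending MindCotine to others, and whether VR side effects were experienced". By contrast, 2.1.3 describes a before-and-after comparison for smoking only: "tobacco use will be compared at two timepoints: Enrollment, and End of treatment". Between the two points, 3.2.2 says "there is no expected contact with the participant until the end of the 6-week period", and under 7.2.4 other events are followed once the team hears of them.

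The adverse-event rules assume a starting value. Section 7.4.1 says "Any pre-existing condition that worsens in severity or frequency should be recorded as a new adverse event", and it defines resolution as Grade 0 or, for a condition already present, return to baseline. Section 7.2.2 requires every recorded event to be judged for relation to the intervention. Adverse events are a secondary endpoint (10.2.2), analyzed as a frequency in the full sample of 20 (10.5.1, 10.5.2).

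**The concern.** The participants are recruited from oncology clinics (3.2.1), and 1.2.4 itself mentions side effects of surgery, radiation and chemotherapy. They may also be using cessation medication and cutting down on cigarettes. Any of these could plausibly produce nausea, dizziness, headache or sweating with no contribution from the headset.

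If the symptoms are rated once and there is no comparator, a patient who was nauseated before enrollment and is still nauseated during a session is recorded in the same way as a patient whom the session made nauseated. At stake is the interpretation of the only structured safety measure in the study. The frequency of reported symptoms may be read as a frequency of VR effects, and the gap cannot be repaired from study ratings once participants have started the app.

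**Working it through.** The plan gives no safety rate, power or error rate to reproduce; N = 20 is the number of free kits (10.1.2). The check is mainly a reading of the text, followed by arithmetic for scale.

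**Step 1. Is there a baseline rating anywhere?** The places where one could appear are:
- Legible screening questions (13.2.1): smoking, other tobacco products, smartphone, availability. No symptom item.
- Enrollment tracking (6.2.1, item 4): demographics, cessation resources wanted, dates. No symptom item.
- Schedule of events (6.1): no symptom assessment in the legible rows.
- Section 10: no baseline symptom variable and no change-from-baseline analysis of symptoms.
- Section 9.4.1: clinical charts are named as source documents, but no step extracts these symptoms from them.

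Screening questions 1, 2 and 5 and parts of the schedule are not legible in the text available. The screen-out script shows that question 1 concerns smoking status and question 5 language; question 2 is unknown. Absence is therefore inferred from all legible text.

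**Step 2. What can the single rating show?** Take one symptom and set the true course beside what item 8 records:

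| Before the app | During app sessions | Item 8 records | Status under 7.4.1 |
|---|---|---|---|
| None | Mild | Mild | New |
| Mild | Mild | Mild | Present, not worsened |
| None | Moderate | Moderate | New |
| Mild | Moderate | Moderate | Worsened, logged as a new event |
| Moderate | Moderate | Moderate | Present, not worsened |

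Rows 1 and 2 give the same answer, as do rows 3 to 5, yet their status under the plan's own rule differs. The wording of item 8 ties the symptom to sessions but does not separate these rows.

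**Step 3. Scale, on an assumption.** The documents give no background prevalence. Let p be an assumed proportion of participants who would have a given symptom without the app. Then the expected number is 20 × p, and the chance of at least one is 1 − (1 − p)^20.

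| Assumed p | 20 × p | 1 − (1 − p)^20 |
|---|---|---|
| 5% | 1 | 0.64 |
| 10% | 2 | 0.88 |
| 20% | 4 | 0.99 |
| 30% | 6 | >0.99 |
| 40% | 8 | >0.99 |

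For each p, 20 × p is an upper bound on the expected number of background cases reported at item 8. It supposes that all 20 use the app, all answer the survey, and everyone with a background symptom reports it as occurring during app use. The item's wording should remove some of these.

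**The case against.** The strongest reply is that item 8 does not ask about symptoms in general. It asks about symptoms during app use, so participants make the link to exposure themselves. The investigator also has other evidence for attribution: clinical charts, the cessation services each participant chose, the end-of-treatment question on quit medication, and app-recorded usage linked to the survey. This stands. A reader might infer that background symptoms and VR effects cannot be told apart at all, or that the causality judgment has no basis; the documents do not support either. Nor is the worsening rule unusable everywhere, since it can be applied where a chart happens to record the symptom.

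Second, 7.4.1 is a logging instruction. It does not define adverse events as worsening only (7.1 and 7.4 define them broadly), and it does not require a baseline-adjusted table. This also stands: a new-or-worse table would be consistent with 7.4.1, not demanded by it.

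Third, the study is a descriptive pilot with limited data collection. No safety rate enters the feasibility metrics in 2.1.4 and 10.2, so an inflated symptom count would change no stated metric, and the bias at issue runs toward overstating harm. This limits the consequence. It does not remove the point, because adverse events are a listed secondary endpoint.

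Fourth, a past-week baseline alone would not match an end-of-treatment question that covers six weeks and only app sessions. That is correct, and the fix has to change both ends. What remains after all four replies is Step 2: one rating cannot show change.

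**Conclusion.** The point holds in a limited form. The legible documents describe one rating of the five symptoms, at end of treatment, with no baseline and no control group. That rating carries a participant-judged time link but cannot reliably separate ongoing symptoms from new or worsened ones. The worsening and return-to-baseline rules cannot be applied to these symptoms from study-collected ratings.

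The adverse-event frequency may therefore overstate VR effects, by an amount that the documents do not allow to be estimated. This takes item 8 responses to feed that frequency, which the plan implies but does not spell out. A reader might take a figure such as 4 of 20 as the expected number of false side effects. It is not: it is an upper bound under an assumed 20% background rate with no source in the documents. The conclusion also assumes that the illegible screening question and schedule cells hold no baseline symptom item. This is an inexpensive improvement to a secondary endpoint; it does not undermine the feasibility assessment.

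**What to change.** 1. At the phone screen or consent step, before the kit is mailed, ask the same five symptoms on the same None-to-Severe scale for the past week.
2. At end of treatment, keep item 8 and add one of two things: a past-week rating on the same scale, or, for each symptom endorsed, a question on whether it was new or worse than before starting the app. The first gives a like-for-like comparison but can miss symptoms that came and went earlier in the six weeks. The second covers the whole period but rests on recall. Choose one before enrollment begins.
3. In 10.5.2, report raw end-of-treatment counts beside new-or-worse counts, and describe this as consistent with 7.4.1.
4. State in 10.5.2 that symptoms from cessation medication or cutting down begun after enrollment are not removed by this comparison.

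The cost is about one to two minutes per participant and one extra table. No change to treatment or eligibility is involved. The baseline rating has to be in place before the first participant starts the app, because it cannot be collected afterwards.
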